3 OBJECTIVES AND ENDPOINTS

OBJECTIVES	ENDPOINTS	JUSTIFICATION FOR ENDPOINTS	PUTATIVE MECHANISMS OF ACTION
Primary			
The primary objective is to understand the outcome of using the at-home intracervical insemination Mosie kit, i.e. pregnancy rate after its use.	The primary endpoints is: Pregnancy Rate after up to 6 cycles. Another primary end point is to understand the rates of pregnancy in people who desire to get pregnant without intercourse (i.e. both single and those in LGBTQ relationships.	The ultimate objective of using the Mosie Kit is to end up pregnant. Thus pregnancy rate is a primary endpoint. Specifically, pregnancy rate in up to 6 (six) cycles will be examined as it is the typical standard timeframe for attempting to get pregnant using IVI or IUI before seeking an alternative method. People who have no known fertility issue who are trying to conceive without intercourse such as those who are in LGBTQ relationships or those who are not in any relationship at all will likely have higher pregnancy rates than those with known fertility issues of female origin. Women in LGBTQ relationships wishing to conceive might also have a higher pregnancy rate than those in heterosexual relationships where infertility might be caused by things like low sperm count, sperm motility issues or erectile dysfunction (ED).	The Mosie Kit is intended to be used to deposit semen at or near the cervix where the sperm will have an increased likelihood of entering the uterus and pairing up with the ovum resulting in a pregnancy. Pregnancy rates increase when sperm reaches the ovum and fertilizes it. In people with no known fertility issues, the Mosie kit deposits the semen where it is able to fertilize the ovum. People without infertility issues who want to get pregnant without sex by using the Mosie Baby are also more likely than people with known fertility issues to get pregnant.

Secondary			

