4 STUDY DESIGN

4.1 Overall Design

This is a post-market retrospective cross-sectional observational study of people using the Mosie Kit for at-home insemination. The goal of the study is to understand the pregnancy rate resulting from using the Mosie Kit of people with known fertility issues or those wishing to conceive without intercourse due to medical reasons such as vaginismus or being in a LGBTQ relationship desiring a child.

This study uses a convenience sample of people who purchased the Mosie Kit in the past 8 complete months prior to the commencement of the study. The complete known list of people will be invited to participate in the study. For the primary hypothesis 1, all study participants will be treated as one group initially. Subsequently, the study participants may be divided into groups according to their age, the type of relationships (heterosexual or LGBTQ), and/or source of infertility to examine the hypothesis as it relates to these subgroups if sufficient sample size indicates this is appropriate; this analysis corresponds to the tertiary hypothesis.

Primary hypothesis 1: Pregnancy rates using the at-home insemination Mosie Kit to deposit semen near or at the cervix (i.e. intracervical insemination) are equivalent or better than traditional in doctor's office intrauterine insemination.

Given the participants can either be people with fertility issues or people in LGBTQ relationships without known problems conceiving or single women wishing to conceive, another primary hypothesis that will be examined is the difference of pregnancy rates in each of these groups. Specifically, the primary hypothesis related to this is as follows:

Primary Hypothesis 2: Pregnancy rates of LGBTQ people or single women using the Mosie Kit where the female has no know fertility issues will be higher than that of heterosexual people with a known fertility cause or those that are designated as having an unexplained fertility issue.

The secondary hypothesis will examine the use of the Mose Kit and its safety as perceived and reported by the study participants. For these hypotheses the participants will be examined as one group as well as categorized by age group and type of relationship. Specifically, the secondary hypothesis will be as follows:

Secondary Hypothesis 1: The participants perceived the Mosie Kit to be easy to use for its intended purpose.

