4.2 Scientific Rationale for Study Design

The retrospective cross-sectional study design was selected because the desire is to examine the pregnancy rates and perception of useability and safety of the Mosie Kit. Since this is a post-market study, the use of an existing group of participants who voluntarily purchased and used the Mosie Kit exists and provides an excellent group of participants to study. The past experiences of these participants will provide valuable information for future participants on the success rate of at-home insemination, information as to the ease of use of the instructions included in the kit, ease of use of the kit, and perceived safety.

The rationale for examining the participants first as a complete cohort and then stratified by type of relationship, infertility source, and age group is that the primary hypotheses relate to overall pregnancy rates using the at-home insemination Mosie Kit and the rate of pregnancy in women without a known fertility cause wanting to get pregnant without intercorse. The type of relationship is also important because a woman in an LGBTQ relationship without fertility issues is more likely to easily get pregnant than a heterosexual female with fertility issues once the semen is deposited at or near the cervix. While there might be LGBTQ women that also have a known cause of fertility, they will be examined by type or relationship as well as by infertility source. Likewise, single women will be categorized by their known infertility source or as not having a known fertility issue. It is important to study the difference between the two groups and explore the impact on the overall pregnancy rate of Mosie Kit users.

Additional hypotheses aim to examine more specifics related to each stratification. For example, age is known to affect fertility rates. Women ages 20-30 are more likely to get pregnant than those in their 40s. The source of infertility may also indicate underlying biological or physical issues that might mediate the pregnancy rates causing different rates of success in each of the groups. All the information obtained through this study will be used to benefit people who are trying to get pregnant and are experiencing infertility issues. Specifically, the study will examine the viability and success rate of at-home insemination.

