9.1 Statistical Hypotheses and General Statistical Approach

The primary objective is to understand the outcome of using the Mosie kit for Intracervical insemination, i.e. pregnancy rate after its use. Specifically the hypothesis is as follows.

Primary hypothesis 1: Pregnancy rates using the at-home insemination Mosie Kit to deposit semen near or at the cervix (i.e. intracervical insemination) are equivalent or better than traditional in doctor's office intrauterine insemination (IUI). Conversely the null hypothesis is that the pregnancy rates using the at-home insemination Mosie Kit to deposit semen near or at the cervix do not have higher rates of pregnancy than in doctor's office IUI.

Analysis: Comparison of total rates of pregnancy using the Mosie Kit to the 10-20% rate reported for IUI by the American Pregnancy Association.

Primary Hypothesis 2: Pregnancy rates of LGBTQ couples or single women using the Mosie Kit where the female has no know fertility issues will be higher than that of heterosexual couples with a known fertility cause or those that are designated as having an unexplained fertility issue. The alternative hypothesis is that people with no known

fertility issues using the Mosie Kit will have less pregnancies than heterosexual couples with known fertility issues.

Analysis: Rate of pregnancy using the Mosie Kit will be obtained for the following groups: LGBTQ couples where carrying female has no known fertility issues, LGBTQ couples where carrying female has a known fertility issue, Heterosexual people with no known fertility issue, Heterosexual people with a known fertility issue, Single females with no known fertility issue and Single females with a known fertility issue. The rates of each group will be analyzed using descriptive statistics and the aggregate of the 3 groups with fertility issues will be compared with the aggregate of the 3 groups without fertility issues. An ANOVA will be used to compare the differences between groups.

Secondary Hypothesis 1: The participants perceived the Mosie Kit to be easy to use for its intended purpose. The alternative hypothesis is that the participants perceive the Mosie Kit to be difficult to use for its intended purpose.

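### The planned analysis of Primary Hypothesis 2 compares different groups from those the hypothesis names

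*Combined protocol and SAP*

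**What the plan says.** Section 9.1 predicts that the pregnancy rate of LGBTQ couples or single women, where the female has no known issue, "will be higher than that of heterosexual couples with a known fertility cause or those that are designated as having an unexplained fertility issue". Section 4.1 carries the same contrast: "Pregnancy rates of LGBTQ people or single women using the Mosie Kit where the female has no know fertility issues will be higher" than in heterosexual people with a known cause or those with unexplained infertility.

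The stated alternative in Section 9.1 is worded differently: people with no known "fertility issues using the Mosie Kit will have less pregnancies than heterosexual couples with known fertility issues". Its first side is no longer limited to LGBTQ and single users, and unexplained infertility has dropped out of its second.

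The analysis paragraph lists LGBTQ, heterosexual and single users, each with and without a known issue, and describes the rate in each. It then says "the aggregate of the 3 groups with fertility issues will be compared with the aggregate of the 3 groups without fertility issues", and ends: "An ANOVA will be used to compare the differences between groups". No planned contrast or pairwise comparison is named.

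Section 9.4.1 sets significance at 0.05, asks for one-tailed tests of directional hypotheses, and refers back to Section 9.1 for the analysis of each hypothesis.

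**The concern.** A primary hypothesis should be decided by a comparison of the groups it names. Here the hypothesis, its stated alternative and its analysis describe three different comparisons, so a reader cannot tell which result would support the claim. The choice could also be made after the rates are known.

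The hypothesised and planned comparisons estimate the same difference if pregnancy rates do not depend on relationship type within fertility status. If they do depend on it, the result for a primary hypothesis is partly driven by users outside its claim. The pooled test could then support a false hypothesis too often, or lose power for a true one.

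**Working it through.** **Text, side by side (Section 9.1)**

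| Group | Hypothesis | Stated alternative | Planned aggregate |
|---|---|---|---|
| LGBTQ, no issue | side 1 | side 1 | side 1 |
| Single, no issue | side 1 | side 1 | side 1 |
| Heterosexual, no issue | not named | side 1 | side 1 |
| Heterosexual, known issue | side 2 | side 2 | side 2 |
| LGBTQ, known issue | not named | not named | side 2 |
| Single, known issue | not named | not named | side 2 |
| Unexplained infertility | side 2 | not named | not placed |

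In the hypothesis, the word *those* before unexplained infertility may mean heterosexual users only or users of any relationship type. On either reading the aggregate adds heterosexual no-issue users and LGBTQ or single users with a known issue. Tertiary Hypothesis 2 lists unexplained infertility among known fertility issues, so its placement needs only a clarification.

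**Does another section supply the contrast?** No. Section 4.2 says of LGBTQ women with a known cause that "they will be examined by type or relationship as well as by infertility source", which defines no comparison. Sections 9.3 and 9.4.2 stratify by relationship type and, in 9.4.2, by infertility issue, as separate factors.

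**The plan's own figure.** Section 9.2 sizes the study on the precision of one proportion: 1.96 × √(0.25/500) = 4.38% (stated as 4.4%) and 1.96 × √(0.25/384) = 5.00% (stated as 5%). Both reproduce, but neither bears on Primary Hypothesis 2, for which no power, effect size or group size is given.

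**Illustration; all cell sizes and rates are assumptions.** Cells: 120 LGBTQ or single without an issue, 250 heterosexual with an issue, 30 LGBTQ or single with an issue, and h heterosexual without an issue, for h = 5, 10, 25, 50, 100. Test: pooled-variance two-proportion z-test, one-sided 0.05, 1,000,000 simulated studies per scenario. The stated contrast compares 120 with 250. The planned aggregate compares 120 + h with 280, and its expected difference is

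(120·p₁ + h·p_h)/(120 + h) − (250·p₂ + 30·p₃)/280,

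where p₁, p_h, p₂ and p₃ are the rates in LGBTQ/single no-issue, heterosexual no-issue, heterosexual issue and LGBTQ/single issue users.

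1. *Hypothesis false* (p₁ = p₂ = p₃ = 25%), p_h = 40%. At h = 50: (30 + 20)/170 − 0.25 = 4.4 points, where the hypothesised difference is 0.
2. *Hypothesis true* (p₁ = 40%, p₂ = 25%), p_h = p₃ = 25%. At h = 50: (48 + 12.5)/170 − 0.25 = 10.6 points instead of 15.
3. *Same fertility effect in every relationship type* (40% v 25%). Both contrasts equal 15 points.

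| | h = 5 | 10 | 25 | 50 | 100 | Stated contrast |
|---|---|---|---|---|---|---|
| (1) pooled difference, points | 0.6 | 1.2 | 2.6 | 4.4 | 6.8 | 0 |
| (1) pooled test supports the hypothesis | 6.5% | 8% | 14% | 27% | 52% | 5% |
| (1) with p_h = 30% | 5% | 6% | 8% | 10% | 14% | 5% |
| (2) pooled difference, points | 14.4 | 13.8 | 12.4 | 10.6 | 8.2 | 15 |
| (2) pooled power | 89% | 88% | 84% | 77% | 64% | 90% |
| (3) pooled power | 91% | 92% | 94% | 95% | 97% | 90% |

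Moving 10 of the 30 LGBTQ/single issue users into the comparator (the wider reading of unexplained infertility) hardly changes the results at h = 10 and h = 50.

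*Effect of the other added group.* With the 30 LGBTQ/single issue users at 10% to 15% and every other cell at 25%, the pooled test supports the false hypothesis in about 8% to 10% of studies even at h = 5.

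**ANOVA.** If it covers all six groups (400,000 simulated studies), its power in scenario 2 is 63% to 67%. It is also significant in 59% to 63% of studies when the difference is reversed (named no-issue groups 25%, all others 40%). A significant F therefore does not by itself support the directional claim.

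**The case against.** The strongest defence is that fertility status, not relationship type, is the intended driver. Section 3 mainly explains the expected difference that way: people without a known issue should conceive more often, and women in LGBTQ relationships might have a "higher pregnancy rate than those in heterosexual relationships where infertility might be caused by things like low sperm count". The stated alternative also drops relationship type from its first side. On that premise the aggregate is valid and somewhat stronger (scenario 3), and the fault lies in a loosely worded hypothesis. This is a fair reading, but the documents do not settle it. Section 4.2 repeats the cross-relationship claim: "a woman in an LGBTQ relationship without fertility issues is more likely to easily get pregnant than a heterosexual female with fertility issues". Tertiary Hypothesis 1 expects higher rates for male-based than for female-based infertility. The LGBTQ issue group is defined by the carrying female, while heterosexual infertility may be male-based, so rates on the issue side may differ by relationship type.

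Second, the heterosexual no-issue group may be nearly empty: the Synopsis expects a history of fertility problems, and Section 4.1 describes users with known issues or those conceiving without intercourse. This limits the size. At 5 to 10 such users the distortion is small, and no passage predicts the rate patterns of scenarios 1 and 2. Section 9.1 nevertheless lists the group, so it cannot be assumed empty.

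Third, the ANOVA may refer to the two aggregates, where it equals a two-sided t-test. The six rates are also reported, so a reversed direction would be visible. Both points stand. On that reading, however, the ANOVA still tests the wrong groups, and it is not one-tailed.

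**Conclusion.** The concern holds. The planned comparison is not the one Primary Hypothesis 2 states, and no other section supplies the stated one. Confidence in this is high because it rests on the text alone.

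The size is conditional on the assumed cells and rates. It is small if few heterosexual users without an issue respond, becomes material from about 25 such users in the less favourable patterns, and disappears if only fertility status matters. The 52% and 64% figures need 100 such users and should not set the weight of the point. It should be fixed before analysis because it decides what a primary result means; the data themselves are unaffected.

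**What to change.** Before the data are analysed, make the hypothesis, its stated alternative and its test agree, in one of two ways.

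- **(a) Test the stated claim.** Pre-specify LGBTQ no-issue plus single no-issue against heterosexual known-issue plus unexplained infertility, and say whether unexplained covers heterosexual users only or all relationship types. Test the difference in proportions one-sided at 0.05, with a matching interval by the same method (two-sided 90%, or a one-sided 95% bound). Under scenario 2, the one-sided test is significant while a two-sided 95% Wald interval includes zero in 7.4% of studies, against 0.1% to 0.2% with a 90% interval. Keep the six-group table and the three-versus-three aggregate as supportive.
- **(b) Reword the hypothesis** as no known issue against any issue, which is what the aggregate tests, and report the no-intercourse groups descriptively.

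Under either option, place unexplained infertility explicitly on the issue side, state which groups the ANOVA compares, and label it supportive.

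Both options change wording only; the survey in Appendix A already asks for relationship type and infertility source. Under (a), respondents outside the named groups do not contribute, power is slightly lower if the fertility effect is common (90% against 91% to 97% above), and relationship type and fertility status change together, so a difference cannot be attributed to either. Under (b), the relationship-type claim is no longer tested. The choice depends on whether that claim is meant to be tested.

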Getting pregnant using IUI can cost \$250-500 per insemination before accounting for the cost of the testing and other imaging done as part of the process. IVF is even more expensive and invasive. According to Katz et al. 2011, the median per-person cost of IVF was approximately \$24,373 (for just IVF) to \$38,015 (for IVF-donor egg). Voorhis et al. 1997 found ICI to cost \$7.800-10,300 while Assisted Reproductive Therapy (ART) cost \$37,00 - 76,000. The cost difference between IVI/ICI, IUI and ART therapies such as IVF is significant. This makes cost a consideration for people attempting to conceive.

The good news is a number of studies such as Cohlen and Ombelet 2014 and Banerjee and Singla 2017, demonstrate the viability of using IVI/ICI as a means of AIH. The benefits of ICI is that it can be done in the privacy of the home, is relatively low cost, and over a 6 cycle time frame seems to have comparable rates to its more expensive counterparts.

Cohlen and Ombelet 2014 showed that for many couples with cervical factor infertility, psychological sexual dysfunction, physiological dysfunction, unexplained infertility and mild to moderate male subfertility using artificial insemination with a husband's sperm (AIH) was a

preferred treatment option. Banerjee and Singla (2017), tested couples with unconsummated marriages due to vaginismus, erectile dysfunction and premature ejaculation. They found 69% of couples ages 20-32, 43% ages 33-36, and 25% over 36 years old conceived using IVI. This is comparable to the expected 10-35% pregnancy rate of IUI.

Additionally, Kop et al. 2018 conducted a literature review to determine if there was a difference between pregnancy rates and live births of IUI versus ICI. They reported that out of six trials totalling 708 women. They concluded that there was not enough evidence to determine that IUI resulted in more live births or pregnancies than ICI.

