Analysis: Descriptive statistics will be used to analyze perceived safety. Qualitative analysis will be used on any comments made related to safety. Rates of vaginal infections will be analyzed using descriptive statistics.

Secondary Hypothesis 5: The majority of participants indicate they have little to no safety concerns related to using the Mosie Kit. Alternative hypothesis is the majority of participants will be very concerned or extremely concerned about the safety of using the Mosie Kit.

Analysis: Descriptive statistics of self-reported level of concern. Additionally, safety measures such as hand washing, disposing of the syringe after use, and reading the instructions will be examined using descriptive statistics.

Tertiary Hypothesis 1: There will be higher pregnancy rates when using the Mosie Kit when the source of infertility is male-based than when it is female-based. The alternative hypothesis is there will be lower pregnancy rates when using the Mosie Kit when the source of infertility is male-based than when it is female-based.

Analysis: In addition to the descriptive statistics a t-test will be run to examine this hypothesis.

Tertiary Hypothesis 2: There is a difference in pregnancy rates of people with known fertility issues depending on the source of their infertility. Specifically, the following sources of infertility will be examined if sufficient data is available.

- o PCOS
- Endometriosis
- Low AMH or low ovarian reserve
- Low sperm count
- Sperm motility issues
- Unexplained infertility
- Erectile dysfunction
- Performance issues or sexual anxiety, or inability to orgasm with partner.

Page 27

- Vaginismus or vulvodynia
- Tilted uterus
- Multiple uterus/cervix
- Loss of a fallopian tube

The alternative hypothesis is that there will be no difference in the fertility rates associated with different sources of infertility.

Analysis: Descriptive statistics, t-test, correlations and multiple ANOVAs will be used to examine this hypothesis.

Tertiary Hypothesis 3: There will be a difference between individuals who perform 2 insemination instances as described in the instructions and those that follow a different schedule or dosage number. The alternate hypothesis is that there will be no difference between the individuals that perform the minimum 2 insemination instances and those that follow difference dosage schedule.

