9.4 Statistical Analyses

9.4.1 General Approach

Statistical analysis will commence with descriptive statistics for each survey question and plotting of the individual data into scatter plots to understand the data distribution. If any information suggests corrective procedures should be employed, the appropriate transformation or non-parametric test will be used.

Categorical values will be reported using descriptive statistics and frequency of occurrence. Key categorical values will also be converted into a percentage of total responses in order to allow an understanding of the prevalence of the response in the sample. For continuous variables, the means with standard deviations, median and range will be reported.

Qualitative data is only expected as a response to two questions, an open ended safety question and an additional comments question. The responses will be evaluated and categorized. Then the frequency of each category will be provided.

For inferential tests such as t-tests and ANOVAs, a p-value of 0.05 and a confidence interval of 95% will be used for statistical significance. The type of hypothesis will determine whether the specific tests will be one-tailed or two-tailed. Hypothesis seeking to understand whether there is or is not a difference will use a two-tailed test while those seeking a greater than or less than relationship will use a one-tailed test. Correlations among some of the variables will also be examined as appropriate.

Statistical analysis process for each hypothesis has already been described in section 9.1. No baseline analysis is used for cross-sectional studies. No interim analyses are planned for cross-sectional one survey studies.

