9.4.3 Exploratory Analyses

Additional exploratory data analysis will be conducted to examine the main characteristics of the data. This analysis will be done using descriptive statistics, scatter plots, and odds ratio. If the exploratory analysis warrants the testing of new hypotheses, t-test or ANOVA may be used for further analysis.

Exploratory modeling will be conducted to examine multiple variables and their relationship to the pregnancy outcome. This will include the source of infertility, age, number of inseminations, number of cycles, lying time, and type of relationship. The model will use correlations and goodness of fit tests in its analysis.

1 0 SUPPORTING DOCUMENTATION AND OPERATIONAL CONSIDERATIONS

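### The tests that decide Primary Hypothesis 2 and Tertiary Hypotheses 1-2 compare crude pregnancy rates, so a difference in age mix between the groups could create or mask a group difference

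*Combined protocol and SAP*

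**What the plan says.** Section 9.1 forms six groups from relationship type (LGBTQ, heterosexual, single) and fertility status (known issue or none). For Primary Hypothesis 2 the "aggregate of the 3 groups with fertility issues will be compared with the aggregate of the 3 groups without fertility issues", and "An ANOVA will be used to compare the differences between groups". For Tertiary Hypothesis 1 (male-based against female-based infertility), "In addition to the descriptive statistics a t-test will be run to examine this hypothesis". Tertiary Hypothesis 2 (source of infertility) uses descriptive statistics, a t-test, correlations and several ANOVAs. None of these entries names a covariate or a stratified test. Section 9.4.1 refers back to 9.1 as the analysis for each hypothesis.

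The protocol treats age as prognostic. Section 4.2 states that "age is known to affect fertility rates". Section 2.2 gives different waiting times before seeking help below and above age 35, and says of a home insemination study: "They found 69% of couples ages 20-32, 43% ages 33-36, and 25% over 36 years old conceived using IVI".

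Age does enter the plan in other places:
- Sections 4.1, 4.2 and 9.3 divide or stratify the data by age, in 4.1 only if sample size allows.
- Section 9.4.2 makes age one of the subgroup factors for all endpoints.
- Section 9.4.3 describes an exploratory model of pregnancy: "This will include the source of infertility, age, number of inseminations, number of cycles, lying time, and type of relationship".

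**The concern.** The groups are self-formed and nothing balances age between them. Expected ages run from about 21 to 50 (synopsis). If the respondents with a fertility issue are older or younger on average than those without, the crude contrast mixes the effect of fertility status with the effect of age. A real difference could be hidden, or an apparent one produced, by age mix alone.

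The age analyses elsewhere do not close this gap. Stratified or subgroup results give one answer per age group. They give no pooled age-adjusted estimate, and no rule says which result decides the hypothesis if the strata and the crude test disagree. The 9.4.3 model is exploratory, is described only as using correlations and goodness-of-fit tests, and is not tied to these hypotheses.

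One of the affected tests is a primary hypothesis. Section 10.1.3 foresees a journal article, use on the sponsor's website and possibly marketing. Section 2.3.2 says the findings should help users decide whether the kit suits them.

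**Working it through.** **The plan's own figure.** Section 9.2 states a 95% margin of 4.4% at 500 surveys and 5% at 384. With p = 0.5, 1.96 × √(0.25/500) = 0.0438 and 1.96 × √(0.25/384) = 0.0500. Both reproduce. They concern one overall proportion; no sample size or power is given for the hypotheses discussed here. That 4.4% is unrelated to the 4.4-point difference below.

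**Inputs from the documents**
- Age-specific conception rates 0.69, 0.43, 0.25 (section 2.2).
- Target 500 surveys (section 9.2).
- Level: "a p-value of 0.05 and a confidence interval of 95% will be used for statistical significance" (section 9.4.1).
- Sidedness: "those seeking a greater than or less than relationship will use a one-tailed test" (section 9.4.1). The ANOVA F-test named for Primary Hypothesis 2 is itself non-directional, so both versions are shown.

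**Assumptions, not in the documents**
- No true group effect: both aggregates have the same rate within each age band.
- 250 respondents per aggregate.
- Age mix centred on equal thirds, with the aggregates differing by s = 10 or 20 percentage points between the youngest and oldest bands.
- A second run with all rates multiplied by 0.4, because the cited rates come from couples with unconsummated marriages.

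**Formulas**
- Mean rate m = (0.69 + 0.43 + 0.25)/3 = 0.4567.
- Difference d = s × (0.69 − 0.25); p1 = m + d/2, p2 = m − d/2.
- SE = √{[p1(1 − p1) + p2(1 − p2)]/250}.
- Two-sided rejection = 1 − Φ(1.96 − d/SE) + Φ(−1.96 − d/SE).
- One-tailed rejection = 1 − Φ(1.645 − d/SE) if the age mix favours the hypothesised group, and 1 − Φ(1.645 + d/SE) if it runs the other way.

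**Worked case, s = 10 points, cited rates.** d = 0.10 × 0.44 = 0.044; p1 = 0.4787, p2 = 0.4347; SE = 0.0445; d/SE = 0.989. Two-sided: 1 − Φ(0.971) + Φ(−2.949) = 0.167.

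| Rates | Shift | Difference | d/SE | Two-sided | One-tailed, mix favours | One-tailed, mix against |
|---|---|---|---|---|---|---|
| Cited | 10 points | 4.4 points | 0.989 | 17% | 26% | 0.4% |
| Cited | 20 points | 8.8 points | 1.983 | 51% | 63% | under 0.1% |
| × 0.4 | 10 points | 1.8 points | 0.509 | 8% | 13% | 1.6% |
| × 0.4 | 20 points | 3.5 points | 1.020 | 17% | 27% | 0.4% |

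**Check by simulation.** 20,000 runs per scenario, with a different starting mix (50/30/20 in one group, the stated shift in the other) and 250 per group:
- Crude two-group ANOVA, cited rates: rejects in 17.4% (10 points) and 51.6% (20 points).
- Same, with a 150/350 split: 14.7% and 44.1%.
- Crude ANOVA with rates halved, 250 per group: 8.8% and 21.2%.
- Mantel-Haenszel test stratified by age band: 4.6% to 5.4% in every scenario, one-sided or two-sided.

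**The case against.** **The plan does deal with age.** A reader might infer that age is ignored. The documents do not support that: sections 4.1, 4.2, 9.3, 9.4.2 and 9.4.3 all use it, and 9.4.3 puts age, infertility source, number of cycles and relationship type into one model. This stands and narrows the point. The defect is that age is absent from the tests that decide the hypotheses.

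**The hypotheses only compare group rates, and a crude difference answers that.** This does not stand. Sections 3 and 4.2 attribute the expected difference to fertility status, so a difference due to age mix would not support the stated reasoning.

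**The size rests on assumptions.** This stands. No age mix or group size is given, and the cited gradient comes from another population. The one-tailed 26% and 63% are tempting headlines, but the named F-test is non-directional, and those figures apply only if the mix favours the hypothesised group. In the other direction false rejection falls below 5% and the risk is of masking a true difference.

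**The fix may need more than wording.** This stands in part. Section 1.3 lists age among the items collected, but section 9.3 allows male respondents and the age item is not legible in Appendix A as available here. Whose age is recorded, and whether in years or bands, cannot be confirmed.

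**The study is a descriptive convenience survey and the tertiary hypotheses are exploratory.** This is fair, and it argues for putting Primary Hypothesis 2 first. It does not remove the gap for a hypothesis labelled primary.

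**Conclusion.** The concern holds in this form: section 9.1 decides Primary Hypothesis 2 and Tertiary Hypotheses 1-2 on crude rates in non-randomised groups, while the protocol itself names age as a driver of pregnancy. Under the stated assumptions, age mix alone raises two-sided rejection from 5% to about 17% or 51% with the cited rates, and to about 8% or 17% with rates scaled by 0.4. These figures illustrate a possibility. They do not predict this survey's result, and the direction of any bias is unknown.

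Three stronger readings are not supported. The documents do not show that the groups differ in age, so one cannot say that the primary contrast will be wrong. They do not show that age is the strongest predictor in the data. And adjusting for age would not make the contrast causal: the number of cycles (up to six) and other conception methods used, both covered by the survey, would still differ between groups.

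**What to change.** - In section 9.1, make an age-adjusted comparison the deciding analysis for Primary Hypothesis 2: logistic regression with age as a covariate, or Mantel-Haenszel over whatever age bands the data provide.
- Use the same adjustment for Tertiary Hypotheses 1-2 where data suffice.
- Report an age-standardised risk difference with its 95% confidence interval, and keep the crude rates as description.
- Confirm that the survey's age item records the age of the person inseminated. If it records only the respondent's age, clarify the item (Appendix A allows questions to be revised for clarity) or restrict the adjusted analysis to respondents who were themselves inseminated.

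The cost is a few lines of analysis text plus, if needed, a small wording change or a somewhat smaller sample for the adjusted contrast. The report should state that age adjustment removes one source of bias only.
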